4.2 Study Design Rationale

The study was designed as comparative, sequential, non-randomized, multi-center, such that each site has an equal number of Subjects in each treatment group, SUI and RUI. The follow-up period of approximately 90 days was selected due to the time required for most Subjects to be able to achieve full leg extension (within $\pm 5^\circ$), a requirement for obtaining suitable weight-bearing hip-to-ankle radiographs for analysis of alignment. The mechanical axis alignment will be assessed at the 3 month follow-up by independent radiographic review. The sequential design (that is at each site all RUI cases will be completed before doing any of the SUI cases) is set up to ensure that with the control group (RUI), current status of OR efficiency is captured rather than this being influenced by any efficiencies learned from use of the SUI.

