8.4.2 Intra-operative Withdrawal

The Investigator may withdraw the Subject intraoperatively for safety reasons, for example, it may become clear that the patient is not suited to receive the implant to be used for the study or the surgeon did not use the assigned instruments for whatever reason. Please refer to table 8-6 for further guidance.

Table 8-6: Intraoperative Withdrawal example

Intraoperative Withdrawal: Potential Subjects to be withdrawn from study participation intraoperatively.		
Example	Action	Follow Up
Intraoperatively determined to be ineligible (example, ATTUNE primary implant not suitable)	Update Screening/Enrollment Log as “Intraoperative Withdrawal” and document reason Submit Subject History, and End of Study/Withdrawal eCRFs to Sponsor Inform Subject that they were withdrawn	Do not continue
Example	Action	Follow-Up
Intraoperatively the assigned instruments are not used to perform the proximal tibia and/or distal femoral resections	Update Screening/Enrollment Log as “Intraoperative Withdrawal” and document reason Submit Subject History, Operative Details, Device Log and End of Study/Withdrawal eCRFs to Sponsor. Submit Adverse Event as applicable. Inform Subject that they were withdrawn	Do Not continue
Intraoperatively the ATTUNE implant is attempted but not retained	Update Screening/Enrollment Log as “Intraoperative Withdrawal” and document reason Submit Subject History, Operative Details, Device Log and End of Study/Withdrawal eCRFs to Sponsor. Submit Adverse Event as applicable. Inform Subject that they were withdrawn	Do Not continue

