### 6.1 CIP Analysis Set Definitions

**Consented/Enrolled Population:** All cases consented to participate in this study.

**Safety Population:** All cases that received the Attune device and the assigned instruments were used.

**Per Protocol Population:** All cases from the Safety Population that did not have major protocol violations.

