### 6.2 Modified Analysis Set Definitions

**Consented/Enrolled Set:** All subjects who consented to participate in the study.

**Safety Set:** All subjects who received an ATTUNE device.

Note: If the treatment instrumentation used for the tibial and femoral cuts differ, the subject will be included in the instrumentation group used for the distal femoral cut. If both SUI and RUI were used for a single cut (tibial or femoral), the subject will be included in the first used instrumentation group. The Safety Set will be used to present results for Demographic, Exploratory Endpoints, and Adverse Events.

**Per Protocol Set:** All Safety Set subjects for whom a single instrumentation type was used and who had no protocol noncompliance evaluated which presents serious risk for the validity or integrity of the clinical trial data and/or regulatory acceptability of the sponsor/study/site; safety or well-being of the subject at risk. The Per Protocol Set will be used to present analyses of the primary and secondary endpoints.

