### **8.4.3 Additional Endpoints (Primary, Safety, or Exploratory)**

#### **Surgeon Satisfaction**

Surgeon satisfaction with the performance of SUI and RUI instrumentation will be assessed on a four-point scale (1=Strongly Dissatisfied, 2=Dissatisfied, 3=Satisfied, 4=Strongly Satisfied) for the following:

- Distal femoral resection instrumentation;
- Proximal tibial resection instrumentation; and
- All ATTUNE TKA instrumentation.

For each of the three satisfaction questions above, analysis will be conducted two ways:

- (1) Summarizing the response to each question as a categorical variable: The tally and percent of times that each response was indicated. This will be summarized overall and by site.
- (2) Dichotomizing the response to determine “Adequate Surgeon Satisfaction” then summarizing by treatment group with counts and percentages. Adequate Surgeon Satisfaction will be derived as “Yes” for responses: “Satisfied” and “Strongly Satisfied” and “No” for responses: “Strongly Dissatisfied” and “Dissatisfied”. Binomial exact 95% CI will be provided for the proportions and fisher’s exact test will be implemented to test the difference between treatment groups.

For each site (surgeon), a line graph will be generated which displays surgeon satisfaction (y-axis) for the site’s first through last case (x-axis).

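### SAP 6.2 analyses an SUI-phase case with an SUI tibial cut and an RUI distal femoral cut as a control, and no table by assigned phase is planned to show it

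*SAP*

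**What the plan says.** SAP 6.2 defines the Safety Set as everyone who received an ATTUNE device and adds a note with two rules for mixed-instrument cases. If the tibial and femoral instruments differ, "the subject will be included in the instrumentation group used for the distal femoral cut". If both instruments were used for one cut, "the subject will be included in the first used instrumentation group". On use, it states: "The Safety Set will be used to present results for Demographic, Exploratory Endpoints, and Adverse Events". The exploratory endpoints in SAP 8.4.3 are surgeon satisfaction (rated separately for the distal femoral instruments, the proximal tibial instruments and the whole set), OR times and procedural obstacles.

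The Per Protocol Set, used for the primary and secondary alignment endpoints, is limited to "All Safety Set subjects for whom a single instrumentation type was used" and no serious noncompliance. SAP 8.7 repeats the primary analysis in the Safety Population.

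The protocol's own Safety Population, restated in SAP 6.1, was narrower: "All cases that received the Attune device and the assigned instruments were used". Protocol Table 8-6 lists as an intraoperative withdrawal the case where "Intraoperatively the assigned instruments are not used to perform the proximal tibia and/or distal femoral resections". It ends follow-up for that subject but still requires the Operative Details and Device Log forms, and an adverse event form where applicable. Under Protocol 4.2, at each site "all RUI cases will be completed before doing any of the SUI cases".

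**The concern.** The grouping follows the instrument used, not the phase in which the subject was treated. A control case is unlikely to switch to SUI, because its site has not yet started SUI study or learning-curve cases. An SUI-phase case can fall back on RUI, which the surgeon already knows. If a problem in an SUI-phase case leads to an RUI femoral cut, the event, the extra time and any recorded obstacle can be tabulated under the control. Those are results that the comparisons of safety, OR efficiency and satisfaction are meant to pick up. Comparing adverse events is a secondary objective, and learning about OR efficiency is the stated reason for not randomizing.

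Nothing planned would show this directly. There is no analysis by assigned phase, and the disposition summary in SAP 8.2 does not count conversions.

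A separate problem concerns satisfaction. The tibial and femoral instruments are rated separately, but each subject carries one group label. If the two cuts used different instruments, one of the two ratings must appear under an instrument it does not describe.

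**Working it through.** **The plan's own figure.** Protocol 10.9 gives 35 per group for 95% power (margin 1.5°, SD 1.870°, one-sided α = 0.05). The noncentrality is 1.5 / (1.87 × √(2/35)) = 3.36 on 68 degrees of freedom, which gives power 0.953. Inflating for 20% loss, 35 / 0.80 = 43.75, rounded up to 44. Both figures reproduce. Only the 44 per group is used below.

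**Conversion patterns for an SUI-phase case, read against the two rules in SAP 6.2.**

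| Pattern | Tibial cut | Distal femoral cut | Group under SAP 6.2 |
|---|---|---|---|
| A | SUI | RUI | RUI (femoral-cut rule) |
| B | RUI | SUI | SUI (femoral-cut rule) |
| C | One cut started with SUI and finished with RUI | Other cut SUI | SUI (first-used rule) |
| D | Started with SUI, finished with RUI | RUI | Rules conflict; no precedence stated |
| E | RUI | RUI | Not addressed; RUI only if grouped by use |

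In row C the switched cut may be either one. Only pattern A clearly moves an SUI-phase case into the control group.

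**Satisfaction items.** In pattern A the rating of the SUI tibial instruments is reported under RUI. In pattern B the rating of the RUI tibial instruments is reported under SUI. One resection rating is misplaced in each, even though B stays in its own phase's group.

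**Illustration for pattern A.** The documents give no conversion rate, so all of these are assumptions: 44 per arm; k pattern-A conversions counted within the 44 and not replaced; each conversion has an adverse event; two other subjects per arm have one.

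- By assigned phase: SUI (2 + k)/44, RUI 2/44.
- By SAP 6.2: SUI 2/(44 − k), RUI (2 + k)/(44 + k).

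| k | Assigned: SUI vs RUI | SAP 6.2: SUI vs RUI |
|---|---|---|
| 0 | 4.5% vs 4.5% | 4.5% vs 4.5% |
| 1 | 6.8% vs 4.5% | 4.7% vs 6.7% |
| 2 | 9.1% vs 4.5% | 4.8% vs 8.7% |
| 4 | 13.6% vs 4.5% | 5.0% vs 12.5% |

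The sign reverses for every k of 1 or more shown. Fisher's exact p stayed above 0.25 under both groupings for k = 1 to 4, with two or with four background subjects per arm; the smallest value was 0.266.

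**OR time.** Assume e extra minutes per conversion and otherwise equal means. The SUI minus RUI difference is +k·e/44 by assigned phase and −k·e/(44 + k) by SAP 6.2. With e = 30, k = 1 gives +0.7 against −0.7 min, and k = 4 gives +2.7 against −2.5 min. With e = 20 and k = 4 it is +1.8 against −1.7 min.

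**The case against.** A reader might infer that SUI cases converted to RUI are in general counted against the control, so that any bias can only favour SUI. The documents do not support that. The first-used rule keeps a case in SUI when a cut is started with SUI and rescued with RUI and the other cut is SUI, which is a natural form of instrument failure. A case with an SUI femoral and an RUI tibial cut also stays in SUI. If an SUI tibial guide fails, RUI completes that cut and RUI then makes the femoral cut, the two rules point to different groups and the SAP does not settle which applies. Nor does the note say that a case abandoned before any SUI cut becomes an RUI case.

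How often pattern A could arise depends partly on the order of the cuts, which is in the surgical technique (Exhibit B), not among the documents reviewed. Conversions may be few: the investigator must judge each subject suitable for either instrument, and about five SUI learning-curve cases per site stay outside the study.

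The consequences are also bounded. Mixed cases are out of the primary and secondary alignment analyses. SAP 5 calls all other endpoint analyses exploratory and rules out labeling claims from them. SAP 8.5 lists every adverse event, and the satisfaction graphs and obstacle listings run in case order within site, which helps to show the phase. Grouping by instrument used is a recognised prespecified choice, and it keeps cases that the protocol's definition dropped.

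All of this stands as a limit on scope and size. It does not remove pattern A, the missing precedence, the missing conversion count or the misplaced satisfaction rating.

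**Conclusion.** The point holds in a limited form. A case in the SUI phase with a wholly SUI tibial cut and a wholly RUI distal femoral cut is analysed as RUI for adverse events, OR times, obstacles and satisfaction. It may also enter the SAP 8.7 sensitivity analysis as RUI, if the Safety Population there means the SAP 6.2 Safety Set and a 3-month radiograph exists. Since Table 8-6 ends follow-up, few such radiographs may exist.

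That reclassification would run mainly from SUI to RUI is an inference from the sequential design, not a stated fact. Its size is unknown. The illustrations show that one to four conversions could reverse the sign of a descriptive contrast, but under assumed event and time burdens, and no test result changed in the scenarios run. With no conversions there is no effect.

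The satisfaction problem needs no assumption about direction: whenever the two cuts use different instruments, one resection rating is reported under the wrong one. Replacing the as-used grouping altogether for safety would be a debatable trade-off, so the case is for adding a table by assigned phase beside it.

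**What to change.** In SAP 6.2 and 8.4.3:

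- Attribute the distal femoral and proximal tibial satisfaction ratings to the instrument used for that resection.
- Present adverse events, OR times, procedural obstacles and overall satisfaction by assigned study phase alongside the as-used grouping, with mixed cases flagged in both.
- State whether the femoral-cut or the first-used rule takes precedence when they disagree, and where a case with both cuts wholly RUI belongs.
- Report the number of conversions per phase.

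The SAP 6.2 Safety Set and the withdrawal entry in Protocol Table 8-6 should also be reconciled, so that it is clear what follow-up data these subjects contribute.

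The cost is SAP wording and one extra set of tables, with no new data collection. The downside is that, in the assigned-phase table, an event caused by RUI after a conversion counts under SUI. The flag makes that visible.

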## 7 Sample Size Justification

The primary endpoint of the difference in group means for the absolute value of mechanical axis alignment will be tested for non-inferiority using a 2-sample t-test and a non-inferiority margin of 1.5° when comparing alignment results obtained using single use instruments to those of reusable instruments. The sample size was established to provide 95% power for a 1-sided test of non-inferiority with  $\alpha = 0.05$  using a pooled standard deviation (SD) of 1.870°. This estimated SD was obtained from a previous DePuy Study (ID # 04023). A sample size of 35 per group was obtained to provide 95% power with a 1-sided alpha of 0.05 and 1:1 treatment allocation. The final sample size was inflated by at least 20% to 44 per group to account for attrition and possible problems with radiographic image quality.

## 8 Analyses to be Conducted

### 8.1 General Conventions

Study data will be tabulated for all subjects in the target analysis population using SAS v9.3 or higher. Planned tabulations are described below and table, figure, and listing shells are provided separately (see [Appendix](#) for file name).

Standard descriptive summaries for continuous data include the number of subjects with nonmissing data (n), mean, SD, median, minimum, and maximum values. For categorical data, the count and percentage will be provided. Percentages will be based on the number of subjects without missing data.

When there is a need to test the significance of a difference between groupings of comparisons of SUI versus RUI which result in a p-value or confidence interval, a t-test will be conducted for continuous variables, and Fishers' Exact Test will be used for categorical variables.

## 8.2 Disposition of Study Subjects

An overall summary of the number of subjects who were (or had): Enrolled, Enrolled but not treated, in the Safety Analysis Set, in the Per Protocol Set, withdrew before study completion, and who completed the study will be tabulated for all sites combined. A listing will be created for completion status and will include columns for all of the items included in the summary table.

## 8.3 Demographic and Baseline Characteristics

Descriptive statistics will be displayed using the subjects in the Safety and the Per Protocol Analysis Populations for:

- Age at consent (in years);
- Gender;
- Race;
- Ethnicity;
- Height (cm);
- Weight (kg);
- BMI ( $\text{kg/m}^2$ ) calculated as  $(\text{Weight in kilograms})/(\text{Height in meters})^2$ ;
- Primary Diagnosis;
- Configuration type (Cruciate Retaining or Posterior Stabilizing);
- Breakdown of Fixed Bearing and Rotating Platform configurations within CR and PS.

Preoperative demographics and baseline characteristics will be compared to determine whether differences exist between treatment groups. Operative details including the type of components implanted, configuration type, and breakdown of FB and RP configurations within CR and PS will be presented without formal comparison.

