2.1 Time and Events Table

Event / Visit	Pre-Op	Surgery	Post-Op
Required Timing (days)	-180d to include day 0	0	30 -150
Discuss Study with Subject	Yes		
Screening Log	Yes		
Informed Consent	Yes		
Enrollment	Yes		
Complete Subject History eCRF	C		
Surgical Procedure 
 Complete Operative Details eCRF Complete Device Log eCRF 		C C	
Radiographs 
 Hip to Ankle Long Film 			R*

 AP View 	R		R

 Lateral View 			R
Complete Adverse Event eCRF		A	A
Complete End of Study/Withdrawal	A	A	C
Advise the Subject when they will next be seen	Yes	Yes	
C= Case Report Form to be completed and submitted in the Electronic data capture system R= Radiograph obtained and submitted R*, For the purposes of this investigation this radiograph will only be performed when the Subject can achieve full leg extension ($\pm 5^\circ$). A= As needed			

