5.2 Exclusion Criteria

Subjects will be excluded from participation if they meet **any** of the following criteria:

- a) The Subject has, in the opinion of the Investigator, a severe deformity that will hinder achieving a mechanical axis alignment target of $0^\circ \pm 3^\circ$.

- b) The Subject has, in the opinion of the Investigator, an existing condition that would compromise their participation and follow-up in this study.
- c) The Subject has, in the opinion of the Investigator, a flexion deformity that will not allow for 0° extension postoperatively.
- d) The Subject is a woman who is pregnant or lactating.
- e) The Subject, in the opinion of the Investigator, is a drug or alcohol abuser (in the last 5 years) or has a psychological disorder that could affect follow-up care or treatment outcomes.
- f) The Subject has participated in a clinical investigation with an investigational product in the last 3 months.
- g) The Subject is currently involved in any personal injury litigation, medical-legal or worker's compensations claims.
- h) The Subject has previous prosthetic knee replacement (any type including unicompartmental, total knee arthroplasty, patellofemoral arthroplasty or ipsilateral UTO/HTO) of the affected knee or a previous patellectomy.
- i) The Subject presents with ankylosis of the hip joint on the side to be treated.
- j) The Subject had a contralateral TKA and that knee was previously entered into the study.^B
- k) The Subject requires simultaneous bilateral total knee replacements.^C
- l) Any case in which Computer-Assisted Surgery (CAS) or TruMatch (or any other type of Custom Patient Instruments) is to be used, or any additional instrumentation are to be used for bone resections that are not provided as part of the ATTUNE RUI or SUI Instrument kits.
- m) The Subject requires a device not specified in the protocol or the surgeon determines that the ATTUNE Knee System is not a suitable treatment.

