8.3.4 Post-operative Management

Immediate post-operative management is at the discretion of the Principal Investigator and should follow each Site's standard of care.

The one(1) postoperative study follow-up visit will be conducted according to the Time and Events Table 2.1. Each Investigator or designee will collect information as noted in Table 8-4 below. At this visit radiographs will be collected as detailed in the Radiographic Protocol (Exhibit F). An independent radiographic reviewer (IRR) will evaluate all radiographs. Copies of the evaluations will be available to Investigators upon request.

Table 8-4: Post-operative Data Collection and eCRFs

Evaluation	Details of Evaluation
Radiographs	For all Subjects post-operative radiographs will be obtained.
End of Study Completion or Subject Withdrawal	For all Subjects the Investigator or designee must complete an End of Study/Subject Withdrawal eCRF to confirm the Subject is no longer in the study.
Post-operative Complication(s) (if applicable)	In the event of a post-operative complication an Adverse Event eCRF is completed. A post-operative complication is defined as a complication that occurs at any time from the time the Subject is in the recovery room up through the time a Subject withdrawal form is submitted ending the Subject's study participation. Complete a separate form for each post-operative complication.

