8.3.6 Management of Bias

To avoid potential bias and ensure consistency, an Independent Radiographic Reviewer (IRR) will be used to evaluate the post-op 90 day radiographs. This is an open investigation by design. Only the independent radiographic reviewer will be blinded regarding the instrumentation. The X-ray images will be provided with all Subject PHI information removed prior to assessment by the IRR. Data from the IRR radiographic evaluations (not the Investigators) will be used for determination of radiographic success criteria. Details of the radiographic assessment and means of submitting radiographs for review are detailed in Exhibit F, the Radiographic Protocol.

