10.2 Treatment Assignment

See Section 7.

Randomization will not be employed in this study. Each site will consecutively enroll all RUI cases prior to enrolling consecutive SUI cases.

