10.10 Analysis Plan

The primary endpoint is a non-inferiority test of mean absolute mechanical axis angle, comparing single use and reusable instrument results with a non-inferiority margin of 1.5° using a 1-sided independent means t-test and $\alpha = 0.05$. The primary endpoint analysis null hypothesis will be rejected and non-inferiority will be concluded if the 1-sided upper 95% confidence limit for $\mu_{SUI} - \mu_{RUI}$ is less than 1.5°.

Preoperative demographics will be compared to determine whether differences exist between treatment groups. Age and BMI will be compared using two-tailed independent means t-tests. Gender distribution will be compared with a Fisher's exact test.

Secondary analyses include:

- Tests of differences for individual component alignment in the frontal and sagittal planes, specifically: distal femoral varus-valgus (FM), proximal tibial varus-valgus (TM), femoral component flexion and tibial slope using (independent means two-tailed t-tests).
- The types and frequencies of adverse events will be tabulated for all enrolled knees. The proportion of each complication will be compared using a Fisher's Exact Test (2 x 2 only) and Chi-square.

Exploratory analyses will be conducted to see if SUI improves OR efficiency compared to conventional (RUI) instruments. Exploratory analyses will also be conducted to investigate OR step times, inter-site differences in OR times, and issues that potentially introduced delays or interruptions in the surgical flow.

The Following Table presents a summary of the planned statistical tests:

Table 10-2: Planned statistical comparisons

Comparison	Purpose	Expected Result
Mean absolute mechanical axis non-inferiority	Primary efficacy	SUI Non-inferior to RUI
Demographic comparisons	Test comparability	No difference
Distal Femoral Varus-Valgus (FM)	Secondary efficacy	No difference
Proximal Tibial Varus-Valgus (TM)	Secondary efficacy	No difference
Femoral flexion	Secondary efficacy	No difference
Tibial slope	Secondary efficacy	No difference
OR Efficiency	Exploratory Analysis	No difference

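### Two sequential, non-randomised phases are compared with an unadjusted t-test; pre-specify a covariate-adjusted sensitivity analysis and report standardised baseline differences

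*SAP*

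**What the plan says.** **Allocation.** Protocol 10.2: "Each site will consecutively enroll all RUI cases prior to enrolling consecutive SUI cases". Protocol 8.3.6 describes an open study in which only the radiographic reader is blinded. The surgeon therefore knows the current phase when judging eligibility.

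**Deformity at entry.** Protocol 5.2(a) excludes, in the investigator's opinion and with no threshold in degrees, patients with "a severe deformity that will hinder achieving a mechanical axis alignment target of" 0° ± 3°. Section 5 also allows a consented, eligible patient to be left out on surgeon preference, under very limited conditions.

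**Primary analysis.** Protocol 10.10 analyses mean absolute mechanical axis angle "using a 1-sided independent means t-test". SAP 7 says that the endpoint "will be tested for non-inferiority using a 2-sample t-test and a non-inferiority margin of 1.5" degrees. Neither names a covariate or a site term. SAP 8.7, the only sensitivity analysis, repeats the analysis in the Safety population.

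**Comparability.** Protocol 10.10 tests age and BMI by t-test and gender by Fisher's exact test. Table 10-2 gives the purpose as testing comparability and the expected result as no difference. SAP 8.3 lists age, gender, race, ethnicity, height, weight, BMI, primary diagnosis and implant configuration, and states: "Preoperative demographics and baseline characteristics will be compared to determine whether differences exist between treatment groups". SAP 5 makes baseline p-values optional and exploratory.

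**Pre-operative alignment.** No measure of it is listed in SAP 8.3 or used in any planned analysis. Protocol 2.1 marks a pre-operative AP view with the code defined as "R= Radiograph obtained and submitted"; the hip-to-ankle film is marked post-operatively only.

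**The concern.** In a randomised trial an unadjusted t-test is protected by the allocation. Here that protection is absent: the arms are two successive groups of patients, admitted by a surgeon who knows which instruments come next. The protocol itself treats deformity as something that can stop the surgeon reaching the alignment target. If milder or harder cases gather in one phase, the difference in mean absolute angle moves with them.

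The plan has no step that would show this. The sensitivity analysis changes the analysis set but leaves the comparison unadjusted. The comparability check is a set of significance tests that will often miss imbalances large enough to matter. If the drift favours SUI, the chance of wrongly declaring non-inferiority exceeds 5%. If it goes against SUI, power is lost.

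**Working it through.** **Inputs from the documents.** SD of the absolute angle 1.87°, margin 1.5°, one-sided α 0.05, 35 evaluable and 44 enrolled per arm (Protocol 10.9, SAP 7).

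**Inputs assumed.** r, the within-arm correlation of a baseline factor with the endpoint; and d, the difference in that factor between phases in SD units. The documents give neither. The main range is r = 0.2 to 0.4 and d = 0.3 to 0.5.

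**1. The plan's own figure.** Standard error at 35 per arm = 1.87 × √(2/35) = 0.447°. Noncentral t with 68 df and noncentrality 1.5/0.447 = 3.36 gives 95.3% power, so the stated 95% is reproduced. At 44 per arm it is 98.2%. The sample size is not in question.

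**2. Power of a baseline t-test** (two-sided 0.05, noncentrality d/√(2/n)):

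| True imbalance | 35 per arm | 44 per arm |
|---|---|---|
| 0.3 SD | 24% | 29% |
| 0.4 SD | 38% | 46% |
| 0.5 SD | 54% | 64% |

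The smallest imbalance found with 80% power is 0.68 SD at 35 per arm and 0.60 SD at 44. More than half of true 0.4 SD imbalances would not reach significance.

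**3. Bias from leaving the factor out.** For a linear relation, bias = r × d × 1.87°.

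- r = 0.2, d = 0.3: 0.2 × 0.3 × 1.87 = 0.11°, and 0.112/1.5 = 7% of the margin.
- r = 0.4, d = 0.5: 0.4 × 0.5 × 1.87 = 0.37°, and 0.374/1.5 = 25% of the margin.

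**4. Effect on the decision at 35 per arm.** Non-inferiority is declared when the observed difference is below about 1.5 − 1.668 × 0.447 = 0.75°.

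- True difference 1.5°, drift favouring SUI: the false-positive rate is the noncentral-t tail with noncentrality bias/0.447. It rises from 5% to 8% (bias 0.11°) or 21% (bias 0.37°).
- True difference 0, drift against SUI: noncentrality is (1.5 − bias)/0.447. Power falls from 95% to 92% or 80%.

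**5. What adjustment does to precision.** With one covariate, the effective SD is about 1.87 × √(1 − r²) × √(1 + d²/4). At 35 per arm:

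- r = 0.1, d = 0.5: SD 1.918°, power 94.5%.
- r = 0.5, d = 0.2: SD 1.628°, power 98.5%.

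Adjustment needs no more patients, but a gain in precision is not guaranteed. With four sites and a two-category diagnosis, the model in the fix has 1 + 1 + 3 + 1 + 1 + 1 + 1 = 9 parameters. That leaves 70 − 9 = 61 residual df at 35 per arm, which is workable.

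**The case against.** The design already limits confounding. One surgeon per site operates in both arms, arm sizes are equal within site, enrolment is consecutive, a screening log documents selection, every patient must be suitable for either instrument set, and severe deformity is excluded in both arms. SAP 8.3 gives descriptive statistics whatever the p-values show. The bias figures rest on assumed r and d, and even the largest is a quarter of the margin.

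Much of this stands. Site is balanced by design, so a site term mainly helps precision. The table of expected results in the protocol is an expectation, not a rule for recording imbalances as absent. But these controls hold surgeon and site constant, not one surgeon's case mix over time. And if the baseline p-values are only optional and exploratory, the plan has no other step that examines confounding.

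Three stronger readings are tempting, and the documents do not support them.

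- *That deformity is not measured at all.* The Radiographic Protocol, the case report forms and the table shells are separate documents. What can be said is that no such measure is listed in SAP 8.3 or used in a planned analysis.
- *That Protocol 8.3.4 and 8.3.6 conflict.* Section 8.3.4 says "An independent radiographic reviewer (IRR) will evaluate all radiographs", and 8.3.6 says "an Independent Radiographic Reviewer (IRR) will be used to evaluate the post-op 90 day radiographs". The first sits in the account of the post-operative visit, directly after the sentence on that visit's films, so the two agree. It also follows that reading the pre-operative films is not already assigned to this reader.
- *That the pre-operative film would settle the matter.* It is an AP view, not a hip-to-ankle film, so it gives only a proxy for the mechanical axis. A signed angle would also be the wrong covariate: varus and valgus deformity may both raise an absolute endpoint, so their effects can cancel in a signed linear term.

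**Conclusion.** The point holds as a gap in the analysis plan. The two phases can differ in case mix, no planned analysis adjusts for that or examines its effect on the result, and baseline tests at this size would miss more than half of 0.4 SD imbalances. Under the assumed r and d the bias is 0.11° to 0.37°. At 35 per arm that corresponds to a false-positive rate of 8% to 21% instead of 5%, or power of 92% to 80% instead of 95%, depending on the direction of drift.

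A reader might infer that the non-inferiority conclusion is likely to be wrong. That does not follow: the direction and size of any drift are unknown, and across this range the bias is well below 1.5°. The consequence is weaker error control and a result that is harder to interpret.

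The remedy is also partial. An ANCOVA corrects only for the factors in the model. Within each site arm and phase coincide, so no model can separate a pure time effect from the instruments. The change is worth making because it costs almost nothing.

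**What to change.** **SAP 8.7.** Pre-specify an ANCOVA of absolute mechanical axis alignment on arm, site, age, sex, BMI and primary diagnosis. Compare the one-sided upper 95% limit for SUI minus RUI with 1.5°, and report it beside the t-test whatever the baseline comparisons show. The t-test stays primary.

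**SAP 8.3.** Report standardised differences for the listed baseline variables instead of p-values.

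Both use data the trial already collects and cost only SAP wording.

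**Optional.** Have the same blinded reader measure coronal alignment on the pre-operative AP films already submitted. Add it to the baseline table and enter it in the model as absolute deviation from neutral, not as a signed angle. This needs about 88 further readings and, because Protocol 8.3.6 assigns the reader the 90-day films, a protocol amendment with IRB/EC approval (Protocol 13.1). The report should state that a knee-level AP film is a proxy and that the adjustment is partial.
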